2.1 Data analysis general information

Following standards are applied for analysis unless otherwise specified.

The data will be analyzed by Novartis. All analyses will be performed by using SAS Version 9.4. It is planned that the data from all centers that participate in this protocol will be used, so that an adequate number of patients will be available for analysis.

All continuous variables will be summarized by simple descriptive statistics (n, mean, standard deviation, median, minimum, maximum). Number and percentage will be presented for categorical data. All statistical tests will be applied at 5% significance level. All presented data will be presented in the form of by-patient listings sorted with treatment dose form and visit (if applicable).

2.1.1 General definitions

Study treatment/ Study drug: The investigational drug whose properties are being tested in the study.

Date of first administration of study drug/treatment: It is defined as the date of first dose of study drug administration to the patient.

Date of last administration of study drug/treatment: It is defined as the date of last dose of study drug administration to the patient.

Study day: Study day is defined as the number of days since the date of first dose of study drug administration. For a particular date, study day is calculated as:

Study day = Assessment date – Date of first dose of study drug administration + 1.

Baseline: Baseline is the last assessment obtained on or before the date of first dose of study drug administration. All assessments obtained after the date of first dose of study drug administration are considered as post-baseline unless otherwise specified.

On-treatment period: The period where the patients are exposed to the study treatment. For this study the treatment phase consists of 28 days of on-treatment period.

Lost to follow-up: The patients whose study completion status is unclear because they fail to appear for study visits without stating an intention to withdraw.

2.2 Analysis sets

In the study protocol, the safety population was predefined as consisting of all patients that enter the study (provide Informed Consent). This was motivated by the fact that the primary focus of this study was not to describe effects of a drug intervention, but to compare the accuracy of two different assessment methods, namely LCI and FEV1. However, a valid assessment of these methods is very difficult in patients without any treatment exposure. Therefore, it was decided to change the definition of the Safety Set

Safety Set: The safety set will consist of all patients that enter the study (provide Informed Consent) and have been exposed to at least one dose of study drug. The Safety set will be used for all analyses.

Table 1-1 Patient classification criteria

Analysis set	Population codes that cause patient to be excluded	Non-PD criteria that cause patient to be excluded
Safety set	1	Did not provide informed consent Did not exposed to at least one dose of study drug

Population code: 0=Include in everything, 1=Exclude from safety set.

2.2.1 Subgroup of interest

All safety analysis will be performed by treatment dose form as Tobramycin inhalation solution (TIS, 300mg/5mL or 300mg/4mL) to be nebulized or as Tobramycin inhalation powder (TIP, 112mg), as prescribed by the treating physician.

2.3 Patient disposition, demographics and other baseline characteristics

Appropriate descriptive statistics for patient disposition, demographic, disease history and baseline characteristics will be presented to describe the study population.

2.3.1 Patient disposition

Total number of patients who were screened, re-screened will be presented by number and percentage for safety set. The summary will be presented for screening phase, end of treatment phase completion and study completion phase. The number and percentage will be presented for patients who treated and entered in the study, who completed the study, who discontinued the study and treatment phase along with reason of discontinuation for safety set by treatment dose form and overall.

Patient identification number and whether they completed the study or discontinued from the study will be listed, along with date of last dose, date of discontinuation/study completion and primary reason of discontinuation by age group and treatment dose form. A Separate by patient listing of all patients along with inclusion and exclusion criteria status will also be provided.

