## **7.1 Information to be collected on screening failures**

Patients may discontinue from the study between Visit 1 and prior to start the first intake of antibiotics in context to the study at Visit 2. These patients are considered screening failures.

Only demography data, occurred SAEs and the primary reason for discontinuation (screening failure log) are collected for those patients who fail to enter the treatment phase. It is not necessary to complete all the required evaluations at the time of discontinuation unless medically indicated.

Potential severe adverse events which may have occurred from time of signing informed consent/written assent until screening failure time should be documented in the patient medical records. Reporting during this time period should be followed as described in Section 8.2.

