### **10.1 Populations for analysis**

The safety set will consist of all patients that enter the study (provide Informed Consent). All analyses will be based on the safety set.

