Treatment emergent adverse events requiring action to be taken with study treatment will be summarized by primary system organ class and preferred term; overall and by treatment dose form.

Treatment emergent adverse events requiring significant additional medication or therapy

Treatment emergent adverse events requiring significant additional therapy (concomitant medication, non- drug therapy) will be summarized by primary system organ class and preferred term; overall and by treatment dose form.

Treatment emergent adverse events outcome

Treatment emergent adverse events with outcome will be summarized by primary system organ class and preferred term; overall and by treatment dose form.

Treatment emergent serious adverse events

Number and percentage of patients with treatment emergent serious adverse events, regardless of study drug relationship, will be presented by primary system organ class and preferred term; overall and by treatment dose form for safety set.

The patient data listing includes, SOC/PT/Verbatim term, start date/study day, end date/study day, the severity of an AE, whether or not an AE is related to MBW or study drug, and whether or not it is a serious AE, action taken with study drug, outcome, duration. Duration will be calculated as end date – start date+1 and for ongoing last visit date – start date+1.

The following patient data listings will be provided by age group and treatment dose form.

1. Treatment emergent serious adverse event
2. Discontinuation due to treatment emergent adverse events

Additionally, listing of all adverse events and treatment emergent adverse event will be provided for safety set by age group and treatment dose form.

TEAE of special interest

Treatment emergent adverse events of special interest(Elevated BUN and Creatinine, Tinnitus and Hearing loss) will be summarized by primary system organ class and preferred term; overall and by treatment dose form.

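### The SAP's dosed-only safety set is also used to count screened patients and to list all adverse events, so screening loss reads as zero and a non-fatal pre-dose SAE in a never-dosed patient has no output

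*SAP*

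**What the plan says.** Protocol 10.1 sets one population: "The safety set will consist of all patients that enter the study (provide Informed Consent). All analyses will be based on the safety set". SAP 2.2 adds a dosing condition. Patients must also "have been exposed to at least one dose of study drug. The Safety set will be used for all analyses". The reason given is that LCI and FEV1 are hard to assess as methods in patients without treatment exposure. SAP section 4 logs the change.

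SAP 2.3.1 then specifies the screening part of the disposition summary: "Total number of patients who were screened, re-screened will be presented by number and percentage for safety set". The same section promises a by-patient listing of eligibility status for all patients. SAP 2.3.2 promises a listing, also for all patients, of exclusions from the analysis set with reasons.

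Protocol 7.1 describes the patients at issue: "Patients may discontinue from the study between Visit 1 and prior to start the first intake of antibiotics" at Visit 2, and they count as screening failures. On what is recorded for them it says: "Only demography data, occurred SAEs and the primary reason for discontinuation (screening failure log) are collected". Protocol 8.2.1 requires SAEs, unlike other adverse events, to be reported from consent onwards.

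For adverse events, SAP 2.8.1 and 2.8.1.1 restrict the SAE table and the SAE listing to treatment-emergent events. One output is wider: "Additionally, listing of all adverse events and treatment emergent adverse event will be provided for safety set". SAP 2.8.2 lists all deaths in the clinical database.

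**The concern.** The screening counts made sense under the protocol's definition, where everyone who consented was in the set. The SAP changed the set but did not carry the change through to 2.3.1 or to the listing of all adverse events. Its reason for the change concerns comparing LCI with FEV1. It supports restricting the efficacy analyses and gives no ground for leaving undosed patients out of a screening count or an SAE listing.

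Two things are at stake in the study report. First, the study is meant to assess the feasibility of LCI (Protocol 2). Patients can be lost before dosing because LCI is below 7.5 (Protocol 5.1). They can also be lost because the central specialist rejects the washout and it cannot be repeated. Protocol 7.4.1 requires withdrawal if a rejected Visit 2 measurement cannot be redone that day, and Protocol section 7 allows that measurement before inhalation. The disposition summary cannot show either kind of loss. Second, Protocol 10.5.2 and SAP 2.8.1.1 count an event as related if it is linked to the diagnostic method as well as to the drug. Multiple-breath washout is scheduled at screening (Protocol Table 7-1), so undosed patients have been exposed to the method under study.

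**Working it through.** **Screened count.** The safety set requires consent and a dose (SAP 2.2). A screening failure leaves before the first dose (Protocol 7.1). The two groups cannot overlap, so within the safety set:

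screened = treated, and screened percentage = treated / treated = 100% for any screening loss.

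The re-screened row likewise covers only patients who were re-screened and later dosed.

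**SAEs.** The question is whether each output can hold a non-fatal SAE that starts after consent in a patient who is never dosed.

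| Output | Restriction in the SAP | Under the protocol's set | Under the SAP's set |
|---|---|---|---|
| SAE table (2.8.1.1) | treatment-emergent | no | no |
| SAE listing (2.8.1.1) | treatment-emergent | no | no |
| Listing of all adverse events (2.8.1.1) | safety set | yes | no |
| Deaths listing (2.8.2) | clinical database | fatal events only | fatal events only |
| Eligibility listing (2.3.1) | all patients | patient shown, no SAE | patient shown, no SAE |
| Exclusion listing (2.3.2) | all patients | patient shown, no SAE | patient shown, no SAE |

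One row changes with the new definition: the listing of all adverse events. It was the only route to an output for such an event.

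**Size.** The documents give no number screened, no screen-failure rate and no pre-dose SAE rate. The planned size is 35, and Protocol 6.6.11 closes recruitment on patients who start study treatment, so screening failures come on top of the 35. (The 28 patients behind that target do reproduce: a paired t-test with change 5 and SD 9 has power 0.809 at n = 28, and 28 / 0.80 = 35. The point does not depend on this.)

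Assume 35 dosed patients and a screen-failure share f. Then consented = 35 / (1 − f) and undosed = consented − 35.

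| f (assumed) | Consented | Undosed | Screened row as specified | Dosed share of consented |
|---|---|---|---|---|
| 10% | 35 / 0.90 = 38.9, about 39 | 4 | 35 of 35, 100% | 90% |
| 20% | 35 / 0.80 = 43.8, about 44 | 9 | 35 of 35, 100% | 80% |
| 30% | 35 / 0.70 = 50 | 15 | 35 of 35, 100% | 70% |
| 40% | 35 / 0.60 = 58.3, about 58 | 23 | 35 of 35, 100% | 60% |

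If, again purely as an assumption, 1% to 5% of undosed patients had an SAE before leaving, the expected number of such patients runs from 3.9 × 0.01 = 0.04 to 23.3 × 0.05 = 1.2.

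**The case against.** Several stronger readings are tempting, and the documents do not support them.

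- A reader might infer that undosed patients disappear from the report. They do not. The eligibility listing would show a failed LCI criterion, and the exclusion listing gives reasons, with non-exposure among the codes in SAP 5.5. The listing of study completion and primary reason for discontinuation in SAP 2.3.1 names no population, although the general rule in SAP 2.2 points to the dosed set. What is lost is the count and its summary.
- A reader might infer that the narrower set removed pre-dose SAEs from the SAE tables. Those tables are treatment-emergent and would omit such events under the protocol's set too.
- A reader might infer harm to representativeness. Protocol 5.1 claims that only for eligible patients, and a patient with LCI below 7.5 is not eligible. The argument could apply only to eligible patients who leave before dosing.
- A reader might infer a broad loss of safety data. On screening failures only SAEs are collected, over a screening period of 5 to 26 days, and they still go to the sponsor within 24 hours (Protocol 8.2.2).

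It is also fair to say that the change of set is disclosed with a reason, and that the mock tables, which may show the layout, are not in the SAP text. SAP 2.3.1 promises a summary for the screening phase, which suggests loose drafting rather than intent. Even so, a programmer following 2.2 and 2.3.1 literally would produce a screening summary without a single screening failure, and nothing in the SAP places the SAE in question in any output.

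**Conclusion.** The point holds as a reporting gap of limited size. The disposition summary will show 100% of screened patients as treated, by definition and at any failure rate. A non-fatal SAE between consent and first dose in a never-dosed patient reaches no output that the SAP specifies; a fatal one may appear in the deaths listing. Both conclusions follow from the SAP's definitions and need no numerical assumption.

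The number of patients is unknown. The range of 4 to 23 rests on an assumed failure rate of 10% to 40% and on 35 dosed patients. Re-screening, allowed by Protocol 5.1, means that failed screenings are not all lost persons. The number of unlisted SAEs may well be zero. The LCI and other efficacy estimates, the treatment-emergent tables and expedited SAE reporting do not change, so the point gives no reason to doubt the primary result.

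**What to change.** - **SAP 2.2:** define an enrolled set of all consented patients alongside the dosed safety set, and limit the statement that the safety set serves all analyses accordingly.
- **SAP 2.3.1:** present screened, re-screened, screen-failed with primary reason, and treated on the enrolled set. LCI below 7.5 and unacceptable washout quality should be separate reasons where recorded; the deviation codes in SAP 5.5 have an entry for the first but none for the second. State whether the rows count persons or screening numbers, and count persons where the database allows the numbers to be linked.
- **SAP 2.8.1.1:** add a listing of all SAEs from consent on the enrolled set, with events before the first dose marked.
- **Unchanged:** efficacy analyses and treatment-emergent tables stay on the dosed set.
- **SAP section 4:** record the addition.

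The cost is one population flag, one revised summary and one listing. Protocol 7.1 already collects the SAEs and the primary reason. Linking re-screened patients may take more work: Amendment 2 lets them take a new number, the documents describe no link between old and new numbers, and Protocol 6.1 keeps the patient list at the site. If no link exists, counting screening numbers and saying so is enough. An SAE from a first, failed screening could then sit under an undosed number even if the person was later treated, and the enrolled-set listing would still show it.

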2.3.2 Protocol Deviation

The number and percentage of patients with protocol deviations will be tabulated by category and deviation for the Safety set; overall and by treatment dose form. Protocol deviations will be listed with date and study day of occurrence, deviation code by age group and treatment dose form for Safety set.

Patient exclusion from analysis set will be listed for all patients with reasons of exclusion (i.e., both protocol and non-protocol deviation).

2.3.3 Demographic characteristics

The following demographic characteristics collected in the CRF at screening will be summarized using the Safety set.

Continuous variables:

- Age (years)
- Height (cm)
- Weight (Kg)
- BMI (Kg/m²)

Categorical variables:

- Age categories(6 to 12 years, >12 to 17years, >17years)
- Sex (Male, Female)
- Race (Caucasian, Black, Asian, Other)
- Ethnicity (Hispanic or Latino, East Asian, Southeast Asian, South Asian, West Asian, Russian, Mixed Ethnicity, Not Reported, Unknown, Other)

Descriptive statistics (n, mean, median, standard deviation, minimum and maximum) will be presented for continuous variables for all patients in the Safety set; overall and by treatment dose form. The number and percentage of patients in each category will be presented for categorical variables. For categorical variables, the patients in the missing category will be taken into account for denominator for calculating the percentage.

Patient demographic data will be listed with date of assessment for safety set by age group and treatment dose form.

2.3.4 Medical history

Medical history will be coded using the Medical Dictionary for Regulatory Activities terminology (MedDRA version 18.1 and above or version used for coding). History/conditions will be summarized for the safety set by primary system organ class and preferred term; overall and by treatment dose form. Verbatim recorded history term will be listed together with the coded terms, date of diagnosis and whether the problem was ongoing by age group and treatment dose form for safety set at start of the study. Separate listing of cystic fibrosis will be presented with date of diagnosis by age group and treatment dose form for safety set.

2.3.5 Surgical and Medical Procedures

All surgical and medical procedures will be summarized for safety set by treatment dose form and overall. Patient data listing will be provided with name of surgery, amount, reason, start date, and end date or ongoing at final exam, sorted with age group and treatment dose form and visit(if applicable).

2.4 Treatments (study treatment, rescue medication, concomitant therapies, compliance)

2.4.1 Study drug Administration

Tobramycin, either as Tobramycin inhalation solution (TIS, 300mg/5mL or 300mg/4mL) to be nebulized or as Tobramycin inhalation powder (TIP, 112mg), as prescribed by the treating physician will be administered to each patient twice daily. Neither TIS nor TIP will be provided to the patient.

The extent of exposure will be examined to determine the degree to which safety can be assessed for Tobramycin, either TIS or TIP. The extent of exposure to study drug will be characterized according to the duration of exposure and the number of patients exposed.

Duration of exposure to the treatment will be calculated as the number of days between the first dose date and the last dose date exposed to that treatment over the specified period, expressed as: Duration of exposure = ((Date of last known dose of study drug – Date of first dose of study drug) + 1. If a substantial number of interruptions occur, additional tables accounting for interruptions may be produced.

The duration of exposure (in days) will be summarized by treatment dose form and overall for the safety set as

- a continuous variable with the standard descriptive statistics, and
- a categorical variable classified into ≤ 14 days, $> 14 - 21$ days, $> 21 - 28$ days, > 28 days with number and percentage of patients in each category.

Patient data listing will be provided along with dose administered(unit), total daily dose(unit), regimen, frequency, start date, study day, end date, dose permanently discontinued, and reason of dose discontinuation by age group and treatment dose form for safety set.

2.4.2 Compliance

Compliance will be assessed by the investigator and/or study personnel at each visit using information provided by the patient via a patient diary. Assessment of compliance will be based on:

- The number of dosing sessions per day (e.g. morning and evening)
- The number of actual days on treatment.

The compliance is defined as the percentage of doses taken by the patient and will be calculated using the following formula:

Compliance (%) = 100 x total study dose consumed by patient/ total study dose patient supposed to consume.

Compliance will be summarized by treatment form and overall for the safety set as

- a continuous variable with the standard descriptive statistics, and
- a categorical variable classified into < 80%, ≥ 80% to < 100%, ≥ 100 to < 120%, ≥ 120%, with number and percentage of patients in each category.

Patient data for compliance will be listed along with date of first/last dose, treatment duration, total dose consumed by age group and treatment dose form for safety set.

2.4.3 Prior, concomitant and post therapies

Rescue medication is any on demand medication at acute clinical deterioration of the patient, independent of the currently used standard therapy.

Prior medications are those concomitant medications which were taken and stopped prior to the first dose of study drug.

Concomitant medications are those concomitant medications which were taken prior to and continued after the first dose of the study drug or those medication which were given at least once between the day of first dose of study treatment and the date of the last study visit.

All prior and concomitant medication will be coded using WHO drug dictionary with updated version. All prior and concomitant medications will be summarized in one table.

The number and percentage of patients taking prior medication, concomitant medications will be presented by ATC class and preferred term; overall and by treatment dose form.

Subject data for prior and concomitant medication will be provided in the form of listing along with medication name, dose, start date/End date of medication, route, frequency, ongoing at final examination and reason by treatment dose form for safety set.

2.5 Analysis of the primary objective

Primary effectiveness analysis will be performed on safety set.

2.5.1 Primary endpoint

The primary variable of this study is the LCI.

The primary effectiveness variable is the time course and changes in LCI from baseline (Visit 2) to Week 4 (Visit 4).

2.5.2 Statistical hypothesis, model, and method of analysis

The primary objective of the study is to evaluate the effectiveness of antibiotic therapy TBM100 in patients with CF aged 6 years and older with mild to moderate lung disease. The effectiveness will be assessed by changes in LCI from baseline to Week 4. Baseline LCI is the assessment taken prior to the start of TBM100, which is typically the value at Visit 2. If baseline value is missing then change is taken from the data recorded at screening. The primary analysis will include patients with a valid observation at baseline and post-baseline visit.

The summary of LCI at baseline, at each post-baseline visit and its change from baseline to each post-baseline visit will be presented using descriptive statistics (n, mean, standard deviation, median, minimum and maximum). Change from baseline will be calculated as value at post-baseline visit minus value at baseline.

Between visits comparison for changes in LCI from baseline will be analyzed using an ANOVA model with factors patient and visit. Estimates over time will be presented as LS-Means, pairwise LS-Mean differences along with 95% confidence intervals and two sided p-values for the pairwise differences between visits.

Additionally, for assessing trend of change in LCI over time, mean values over time and the raw LCI values over time for each patient will be displayed graphically for each respective visit. All analysis mentioned in this section will be done for safety set at 5% significance level.

All efficacy data will be listed with date of assessment by age group and treatment dose form.

